7.4.3.1 Primary Efficacy Endpoint

Absolute change from Baseline in total atrophic acne scar count at Week 24 will be summarized by treatments using descriptive statistics. The bilateral difference between products in absolute change from Baseline in total atrophic acne scar count at Week 24 will be summarized using descriptive statistics and will be analyzed on the ITT population using the Student's t-test for paired samples. The point estimate of the mean difference and the related 95% confidence interval will be presented. Assumption of normality will be checked. If normality assumption is not met, the appropriate non-parametric statistical methods will be used. PP analysis will be also performed to assess the robustness of the results obtained on the ITT population.

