### 4 SAMPLE SIZE CONSIDERATION

The sample size calculation is based on the results of the study RD.06.SPR.118295 "A Multi-Center Study to evaluate Subject Reported Outcomes with use of trifarotene 50  $\mu$ g/g cream in the treatment of moderate facial and truncal acne vulgaris" and of the study RD.03.SPR.105061 "Effect of Adapalene 0.3% - Benzoyl Peroxide 2.5% gel versus vehicle gel on the risk of formation of atrophic acne scars in moderate to severe acne subjects".

In study RD.06.SPR.118295, the following results were obtained for the absolute change from baseline in total atrophic acne scar count at week 24:

These results refer to a whole face treatment whilst in the current study a split-face design is used. Moreover, due to the lack of a Vehicle arm, it is not possible to estimate the mean value and the variability of the difference in mean absolute change from baseline in total atrophic acne scar between treatment arms.

It is possible to hypothesize that the mean reduction in trifarotene 50  $\mu$ g/g cream arm when only half-face is treated is -1.7 but there are no data for estimating the variability of the difference between trifarotene 50  $\mu$ g/g cream and vehicle cream.

In study RD.03.SPR.105061 a split-face design was used and the following results were obtained for the absolute change from baseline in total atrophic acne scar count at week 24:

CCI

Under the following hypotheses:

- Mean absolute change from baseline in total atrophic acne scar count at week 24 for trifarotene 50 μg/g cream is -1.7
- Mean absolute change from baseline in total atrophic acne scar count at week 24 for Vehicle cream is zero
- Difference absolute change from baseline in total atrophic acne scar count at week 24 between trifarotene 50 μg/g cream and vehicle cream is -1.7
- Variability of the difference between trifarotene 50 μg/g cream and vehicle cream is 6.0 (derived by supposing an increase of about 35% of the variability observed in study RD.03.SPR.105061)

the sample size for a Student's t-test for paired samples can be calculated according to the following formula:

$$n \ge \frac{\left(t_{\frac{1-\alpha}{2},n-1} + t_{1-\beta,n-1}\right)^2 \sigma_{Diff}^2}{\left(\mu_{Trifarotene} - \mu_{Vehicle}\right)^2}$$

where  $t_{p,v}$  is the Student's t distribution quantile with v degrees of freedom and probability p (n is rounded up to the closest integer).

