### 6.1.5 Statistical Tests and Confidence Intervals

A two-sided type I error  $\alpha = 0.05$  will be used to declare statistical significance for the primary endpoints and the secondary endpoints. Confidence intervals (CIs) will be two-sided with 95% coverage for the primary endpoint and the secondary endpoints. The following flagging conventions will be applied for the p-values of all statistical testing:

- $0.01 \le \text{p-values} < 0.05 \text{ will be flagged with one asterisk (e.g. "0.0499 *")}$
- $0.001 \le \text{p-value} \le 0.01$  will be flagged with two asterisks (e.g. "0.0099 \*\*")
- $0.0001 \le \text{p-value} < 0.001 \text{ will be flagged with three asterisks (e.g. "0.0009 ***")}$
- p-value < 0.0001 will be flagged with four asterisks (e.g. "< 0.0001 \*\*\*\*")

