### 6.3.3 Analysis of Primary Endpoint

The hypothesis test for the primary endpoint can be formally defined as follows:

$$\begin{cases} H_0: \mu_{Diff} = 0 \\ H_a: \mu_{Diff} \neq 0 \end{cases}$$

where  $\mu_{Diff}$  is the mean of the differences in change from baseline in total atrophic acne scar count at Week 24 between the trifarotene 50  $\mu$ g/g side and the vehicle side.

The hypothesis test for the primary endpoint will be evaluated on the ITT population at the two-sided significance level  $\alpha = 0.05$ . Efficacy will be claimed if the between treatment difference on the primary endpoint is statistically significant with a p-value < 0.05.

The bilateral difference between the trifarotene side and the vehicle side in absolute change from baseline in total atrophic acne scar counts at Week 24 will be analyzed on the ITT population using the Student's t-test for paired samples. The point estimate of the mean difference and the related 95% confidence interval will be presented. Assumption of normality will be checked. If normality assumption is not met, the appropriate non-parametric statistical method (Wilcoxon signed rank test, Hodges-Lehmann estimate of location shift and asymptotic confidence interval) will be used.

For analysis of change from baseline in total atrophic acne scar counts to Week 24, missing counts will be imputed using Multiple Imputation (MI) under the Missing At Random (MAR) assumption. It is expected that the pattern of missing data will be monotonic, with slight deviations being corrected by the Markov Chain Monte Carlo (MCMC) method of the SAS MI procedure. Separate imputations by treatment group will be carried out. Linear regression will be employed to model the missing acne counts, with the following covariates included in the imputation model: non-missing total atrophic acne scar counts from earlier time points (see Section 6.3.6.2 for further details).

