### CONFIDENTIAL

Page 49 of 59 Final version 2.0, 27FEB2023

No hypothesis test will be evaluated for the rest of the secondary efficacy endpoints. p-values and 95% confidence intervals will be presented for descriptive purposes only.

The bilateral difference between the trifarotene side and the vehicle side in absolute change from baseline in total atrophic acne scar counts at Week 1, 2, 4, 8, 12, 16 and 20 will be analyzed on the ITT population using the Student's t-test for paired samples. The point estimate of the mean difference and the related 95% confidence interval will be presented. Assumption of normality will be checked. If normality assumption is not met, the appropriate non-parametric statistical method (Wilcoxon signed rank test, Hodges-Lehmann estimate of location shift and asymptotic confidence interval) will be used.

The bilateral difference between the trifarotene side and the vehicle side in percent change from baseline in total atrophic acne scar count at each post-baseline visit will be analyzed on the ITT population using the Student's t-test for paired samples. The point estimate of the mean difference and the related 95% confidence interval will be presented. Assumption of normality will be checked. If normality assumption is not met, the appropriate non-parametric statistical method (Wilcoxon signed rank test, Hodges-Lehmann estimate of location shift and asymptotic confidence interval) will be used.

For analysis of change from baseline in total atrophic acne scar counts to Weeks 1, 2, 4, 8, 12, 16 and 20, missing counts will be imputed using Multiple Imputation (MI) under the Missing At Random (MAR) assumption. It is expected that the pattern of missing data will be monotonic, with slight deviations being corrected by the Markov Chain Monte Carlo (MCMC) method of the SAS MI procedure. Separate imputations by treatment group will be carried out. Linear regression will be employed to model the missing acne counts, with the following covariates included in the imputation model: non-missing total atrophic acne scar counts from earlier time points (see Section 6.3.6.2 for further details).

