### 6.3.6.2 Handling of Dropouts or Missing Data

Missing data for atrophic acne scar counts will be imputed using Multiple Imputation (MI) under the Missing At Random (MAR) assumption. The following steps will be followed:

- 1. The missing data pattern of atrophic acne scar counts will be evaluated. If the pattern is non-monotone, the MCMC method of SAS PROC MI will be used to make it monotone. The single chain method will be used, with 200 burn-in iterations and 100 iterations between imputations. In case of lack of convergence with the single chain method, the multiple chain method will be used. Separate imputations by treatment group will be carried out. The minimum values for imputed variables will be set to 0, in order to force PROC MI to redraw another value for imputation when an intended imputed value is less than the 0. Imputed values will be rounded to the nearest integer. The seed number will be set to 202395 and fifty (50) imputations will be created.
- 2. SAS PROC MI will be used for imputing missing values of data with monotone missing pattern. If the MCMC method of step 1 was previously employed, one imputation will be made using each of the fifty (50) MCMC-imputed datasets. If the MCMC method of step 1 was not previously employed, fifty (50) imputations will be created assuming the data are Missing At Random. The seed number will be set to 202395. A linear regression model will be used with covariates for non-missing atrophic acne scar counts from earlier scheduled time points

including baseline. In case of lack of convergence with linear regression model, a predictive mean matching method will be used. Separate imputations by treatment group will be carried out. The minimum values for imputed variables will be set to 0, in order to force PROC MI to redraw another value for imputation when an intended imputed value is less than the 0. Imputed values will be rounded to the nearest integer. Absolute and percent change from baseline in atrophic acne scar counts will be derived from the corresponding imputed lesion counts.

- 3. The imputed datasets will be analyzed as specified in sections 6.3.3 and 6.3.5.
- 4. The resulting analysis on the imputed datasets will then be combined to produce a single set of statistics using PROC MIANALYZE.

The number of fifty (50) imputations was selected in order to prevent a power falloff due to choosing a number of imputations too small [1].

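### An unspecified normality check decides whether the t-test or the Wilcoxon test carries the primary claim, although the hypothesis and the sample size concern the mean

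*SAP*

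**What the plan says.** SAP 6.3.3 sets the null and alternative on a parameter that "is the mean of the differences in change from baseline in total atrophic acne scar count at Week 24 between the trifarotene" side and the vehicle side. SAP section 4 sizes the trial on the same quantity: "the sample size for a Student's t-test for paired samples can be calculated according to the following formula". The blinded re-estimation in SAP 4.1 uses the same formula. The success rule is "Efficacy will be claimed if the between treatment difference on the primary endpoint is statistically significant with a p-value < 0.05".

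SAP 6.3.3 then makes the test conditional: "Assumption of normality will be checked. If normality assumption is not met, the appropriate non-parametric statistical method" is used, which the SAP names as the Wilcoxon signed rank test with a Hodges-Lehmann shift and an asymptotic interval. SAP 6.3.5.1 repeats the condition for Weeks 1 to 20, and these visits form the seven-step fixed sequence in SAP 6.3.6.5. Protocol 7.4.3.1 has the same condition but does not name the fallback: "If normality assumption is not met, the appropriate non-parametric statistical methods will be used".

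SAP 6.3.6.2 creates 50 imputed datasets, analyses each as in 6.3.3 and 6.3.5, and ends: "The resulting analysis on the imputed datasets will then be combined to produce a single set of statistics using PROC MIANALYZE". The sensitivity analyses in SAP 6.3.4 cover missing data and the per-protocol set. None keeps the t-test alongside Wilcoxon if the switch happens.

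**The concern.** The check has no stated test, cut-off or dataset (observed cases, or each imputed dataset). It is made on trifarotene-minus-vehicle differences, which SAP 4.1 itself says cannot be calculated without unblinding the sides. So the p-value that carries the efficacy claim is settled only once the treatment-signed data are visible, by a criterion the SAP leaves open.

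The two tests also answer different questions. When paired differences are skewed, the signed rank test addresses the pseudo-median, not the mean in the stated hypothesis. A switch can then cost power, add power, or reject when the mean is zero, depending on the shape. The hierarchy could use one test at one visit and the other at the next.

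**Working it through.** **1. The plan's own figure.** Inputs from SAP section 4 and Table 8: two-sided alpha 0.05, power 80%, mean difference -1.7, SD of the difference 6.0, 15% drop-out. Formula: n ≥ (t[0.975, n-1] + t[0.80, n-1])² × SD² / difference². At n = 100 the right-hand side is 99.73, so n = 100. Noncentral-t power at 100 pairs is 80.1%. Then 100 / 0.85 = 117.6, so 118 randomised. The stated 100 and 118 reproduce for a paired t-test on the mean.

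**2. The criterion matters.** The SAP names no check, so three common ones were tried at 0.05 on 100 rounded differences with mean -1.7 and SD 6. The share of trials that switch to Wilcoxon was:

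| Shape | Jarque-Bera | Shapiro-Wilk | Lilliefors |
|---|---|---|---|
| Normal | 4% | 7% | 23% |
| Mild skew (gamma, shape 8) | 58% | 77% | 74% |

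**3. Power of the rule as written.** Assumptions: 100 pairs, SD 6, mean -1.7, rounded differences, Shapiro-Wilk at 5%, a few thousand simulated trials per shape. The two-stage rule uses Wilcoxon when the check fails and the t-test otherwise. Negative values favour trifarotene.

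| Shape of the differences | Switch rate | Power of two-stage rule |
|---|---|---|
| Normal | about 8% | about 80% |
| t, 6 df (symmetric, heavy tails) | about 51% | about 83% |
| Skewness -1 (long tail towards benefit) | about 97% | about 59% |
| Skewness +1 (long tail away from benefit) | about 97% (mirror image) | about 92% |
| 20% strong responders | about 21% | about 76% |

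The t-test had about 78 to 82% in all five. Reruns move single entries by a point or so.

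**4. The quantity moves.** With mean -1.7 and skewness -1, the Hodges-Lehmann target is about -1.25, so a switch estimates a smaller shift than the one powered. By symmetry, skewness +1 moves it the other way by the same 0.45, to about -2.15.

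**5. Rejection at a zero mean.** With symmetric differences, both the rule and the t-test reject in about 5 to 6% of trials. With mean zero and skewness of 1 in either direction, the rule rejects in about 11 to 12% and the t-test in about 5%.

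**6. Pooling.** PROC MIANALYZE combines an estimate with its standard error. The mean difference supplies both. A Hodges-Lehmann estimate can, if its standard error is taken from the asymptotic interval (width divided by 2 × 1.96). The signed-rank p-value, to which the success rule would apply after a switch, is not such a pair, and SAP 6.3.6.2 gives no rule for it. Nor does it say which test applies if some of the 50 datasets pass the check and others fail.

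**The case against.** Several points on the other side are sound and limit the claim.

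- A reader might infer that the sponsor is free to choose a test after seeing results. The documents do not support that: the SAP names both tests, the estimator and the interval, and the protocol already carried the conditional rule. What is open is the trigger.
- A reader might infer that the Wilcoxon branch cannot be pooled at all. That is too strong, because Hodges-Lehmann can be pooled as in step 6. What is missing is a stated method, above all for the p-value.
- A reader might infer a general inflation of type I error. If trifarotene changes nothing in any subject, random assignment of sides makes the differences symmetric about zero, and both tests hold near 5%. The excess needs a zero mean with skewed differences.
- A switch need not cost power. It gains under heavy tails and under skewness +1, and no document says which shape to expect. Even with 20% strong responders, Wilcoxon alone has about 72% but the rule has about 76%, because the check seldom fires.
- SAP 6.3.3 promises the mean difference and its interval before the fallback sentence, so the powered quantity may still be shown.
- SAP section 8 places further analysis detail, including code, in separate shells that are not among the documents. They may define the check.

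None of this removes the mismatch: the claim rests on a p-value, and after a switch that p-value no longer tests the stated mean hypothesis when differences are skewed. A rule that decides the primary test belongs in the SAP itself.

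**Conclusion.** The concern holds as a mismatch between the stated hypothesis and the test that may carry it, together with an unstated trigger and an unstated pooling rule. Under the assumed check and shapes, the rule's power runs from about 59% to 92% around a planned 80%, while the t-test stays at 78 to 82%. Its rejection rate at a zero mean is about 11 to 12% with skewness of 1, and about 5 to 6% under symmetry.

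These figures illustrate and do not predict. They rest on Shapiro-Wilk at 5%, 100 pairs, SD 6 and the shapes listed, and they analyse one complete dataset per trial rather than 50 imputations. The firm part needs no simulation: hypothesis, sample size and re-estimation are all on the mean, and the switch leaves the mean. The figures of 100 evaluable and 118 randomised are correct for the t-test.

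**What to change.** In SAP 6.3.3 and 6.3.5.1, make the paired t-test on the mean difference the primary and hierarchical test whatever the normality check shows, and pool the mean difference and its standard error over the 50 imputations. Keep Wilcoxon and Hodges-Lehmann as a named sensitivity analysis with its pooling stated: for example, Hodges-Lehmann with the standard error from its asymptotic interval, or observed cases only.

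The same condition stands in Protocol 7.4.3.1, 7.4.3.2 and the synopsis. Align those, or document the departure under SAP section 7. Either should be done before unblinding.

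The cost is wording. The sample size stays at 100 evaluable and 118 randomised, with 80.1% power. The price is Wilcoxon's power gain if the differences turn out heavy-tailed or skewed in the direction that favours it. Making Wilcoxon the powered test instead would, under normal differences (relative efficiency 3/π = 0.955), need 100 / 0.955 = 104.7, so 105 evaluable, and 105 / 0.85 = 123.5, so 124 randomised. The hypothesis would also have to be rewritten.

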### 6.3.4 Sensitivity Analysis of Primary Endpoint

To assess the robustness of the primary efficacy results, the following sensitivity analyses will be conducted:

- 1) Jump-to-Reference (J2R) approach under Missing Not At Random (MNAR) assumption, by imputing missing differences between treatments as zero (0);
- 2) Missing data of primary endpoint will be imputed using Last Observation Carried Forward (LOCF);
- 3) Observed Case (OC) analysis;
- 4) Per Protocol (PP) analysis.

### 6.3.5 Analysis of Secondary Endpoints

### 6.3.5.1 Atrophic Acne Scar Counts up to Week 20

The hypothesis test for the absolute change in total atrophic acne scar count per half-face from Baseline up to Week 20 can be formally defined as follows:

$$\begin{cases} H_0: \mu_{Diff} = 0 \\ H_a: \mu_{Diff} \neq 0 \end{cases}$$

where  $\mu_{Diff}$  is the mean of the differences between the trifarotene 50  $\mu g/g$  side and the vehicle side at Week 1, 2, 4, 8, 12, 16 and 20.

The hypothesis tests for the absolute change in total atrophic acne scar count per half-face from baseline up to Week 20 will be evaluated on the ITT population at the two-sided significance level  $\alpha = 0.05$  (the management of multiplicity is described in Section 6.3.6.5).

Study Number 202395 Statistical Analysis Plan

### CONFIDENTIAL

Page 49 of 59 Final version 2.0, 27FEB2023

No hypothesis test will be evaluated for the rest of the secondary efficacy endpoints. p-values and 95% confidence intervals will be presented for descriptive purposes only.

The bilateral difference between the trifarotene side and the vehicle side in absolute change from baseline in total atrophic acne scar counts at Week 1, 2, 4, 8, 12, 16 and 20 will be analyzed on the ITT population using the Student's t-test for paired samples. The point estimate of the mean difference and the related 95% confidence interval will be presented. Assumption of normality will be checked. If normality assumption is not met, the appropriate non-parametric statistical method (Wilcoxon signed rank test, Hodges-Lehmann estimate of location shift and asymptotic confidence interval) will be used.

The bilateral difference between the trifarotene side and the vehicle side in percent change from baseline in total atrophic acne scar count at each post-baseline visit will be analyzed on the ITT population using the Student's t-test for paired samples. The point estimate of the mean difference and the related 95% confidence interval will be presented. Assumption of normality will be checked. If normality assumption is not met, the appropriate non-parametric statistical method (Wilcoxon signed rank test, Hodges-Lehmann estimate of location shift and asymptotic confidence interval) will be used.

For analysis of change from baseline in total atrophic acne scar counts to Weeks 1, 2, 4, 8, 12, 16 and 20, missing counts will be imputed using Multiple Imputation (MI) under the Missing At Random (MAR) assumption. It is expected that the pattern of missing data will be monotonic, with slight deviations being corrected by the Markov Chain Monte Carlo (MCMC) method of the SAS MI procedure. Separate imputations by treatment group will be carried out. Linear regression will be employed to model the missing acne counts, with the following covariates included in the imputation model: non-missing total atrophic acne scar counts from earlier time points (see Section 6.3.6.2 for further details).

### 6.3.6 Statistical/Analytical Issues

### **6.3.6.1** Adjustments for Covariates

No adjustment for covariates is planned for the primary, secondary and exploratory efficacy analyses.

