### Notes:

- 1) Scar severity grading (SGA) and scar counts will be performed separately. The scar severity assessment will be performed before the scar counting.
- 2) Acne severity grading (IGA) and acne lesion counts will be performed separately. The acne severity assessment will be performed before the acne lesion counting.

[figure not shown]
Throughout the study when possible, the same evaluator should perform the SGA, scar counts, IGA and acne lesion counts, for each subject. In the event there is a change in the assigned evaluator for a given subject, the reason for change should be documented. If it is not possible to use the same evaluator to follow a given subject, evaluations between the primary and subsequent evaluator should overlap (both evaluators should examine the subject together and discuss findings) for at least one prior visit. At the final study visit (Week 24 or Early Termination), attempts should be made for the rater to be the same as baseline for the following assessments, to the extent possible:

[figure not shown]

[figure not shown]
For all efficacy assessments, the zone in the middle of the face (approximately 2 cm wide and inclusive of the nose) should be excluded for clinical efficacy evaluation because subjects may apply a mix of investigational products in this area (Figure 2).

1.0

Study Number 202395 CONFIDENTIAL Page 24 of 59
Statistical Analysis Plan Final version 2.0, 27FEB2023

[figure not shown]

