### **CONFIDENTIAL**

Page 33 of 59 Final version 2.0, 27FEB2023

$$\overline{D^2} = \frac{1}{n_1} \sum_{j=1}^{n_1} D_j^2$$

is the mean of squared differences. Without unblinding the treatment assigned to each half face, we can calculate the Left-Right difference as follows:

 $LR_i = XLeft_i - XRight_i$ 

Since

$$|LR_i| = |D_i|$$

the mean of squared differences can be re-calculated as follows:

$$\overline{D^2} = \frac{1}{n_1} \sum_{j=1}^{n_1} D_j^2 = \frac{1}{n_1} \sum_{j=1}^{n_1} LR_j^2 = \overline{LR^2}$$

and the following conditions hold for the mean of differences and the squared mean of differences

 $-\overline{|LR|} \le \overline{D} \le \overline{|LR|}$ 

and

$$0 \le \overline{D}^2 \le \overline{|LR|}^2$$

where

$$\overline{|LR|} = \frac{1}{n_1} \sum_{i=1}^{n_1} |LR_i|$$

is the average of the absolute values of the Left-Right differences.

According to the previous formulas, the following boundaries can be calculated for observed variance after n1 subjects:

$$\frac{n_1}{n_1-1} \Big(\overline{LR^2} - \overline{|LR|}^2\Big) \leq S_{Obs}^2 \leq \frac{n_1}{n_1-1} \overline{LR^2}$$

The observed variance after  $n_1$  subjects can be estimated as follows:

$$S_{Obs}^2 = \frac{n_1}{n_1 - 1} \overline{LR^2}$$

Missing squared differences of atrophic acne scar counts between the left and right sides of the face at Week 24 will be imputed using multiple imputation methodology (as specified in section 6.3.6.2). A linear regression model will be used with covariates for non-missing squared differences of atrophic acne scar counts between the left and right sides of the face from earlier scheduled time points including baseline.

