### 6 STATISTICAL METHODS AND DATA CONSIDERATIONS

### **6.1** General Considerations

### 6.1.1 Baseline

For statistical analyses purpose, baseline is defined as the last non-missing measurement prior to the first treatment for subjects treated and as the last non-missing measurement prior to randomization for subject randomized but not treated.

Absolute change from baseline and percent change from baseline will be calculated as follows:

Absolute Change from Baseline - PostBaseline - Baseline

$$Percent \ Change \ from \ Baseline = \begin{cases} Baseline \neq 0 \Rightarrow 100 \cdot \frac{PostBaseline - Baseline}{Baseline} \\ Baseline = 0 \Rightarrow Missing \end{cases}$$

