# 10-Jul-2023 00:00:00

### 6.2.5 **Demographic and Other Baseline Characteristics**

Descriptive statistics (n, mean, standard deviation, median, first and third quartile, min and max) or frequencies and proportions (n, %) of subjects for each classification category (as applicable) will be presented using the ITT population for the following demographic data and baseline characteristics:

- Age (years)
- Age Groups
  - <18 years old
  - ≥18 years old
- Sex
  - Male
  - Female
- Ethnicity
  - Hispanic or Latino
  - Not Hispanic or Latino
  - Not Reported
- Race
  - White
  - Black or African American
  - Asian
  - American Indian or Alaska Native
  - Native Hawaiian or Other Pacific Islander
  - Other
  - Multiple
- Body weight at Screening (kg)
- Fitzpatrick Skin Type
  - Type I
  - Type II
  - Type III
  - Type IV
  - Type V
  - Type VI

- Baseline Investigator Scar Global Assessment (SGA) by treatment side (trifarotene 50 μg/g versus vehicle)
  - 0 Clear
  - 1 Almost Clear
  - 2 Mild
  - 3 Moderate
  - 4 Severe
- Baseline Total Atrophic Acne Scar Counts by treatment side (trifarotene 50 μg/g versus vehicle)
- Baseline 2-4 mm Atrophic Acne Scar Counts by treatment side (trifarotene 50 μg/g versus vehicle)
- Baseline >4 mm Atrophic Acne Scar Counts by treatment side (trifarotene 50 μg/g versus vehicle)
- Baseline Investigator Global Assessment (IGA) by treatment side (trifarotene 50 μg/g versus vehicle)
  - 0 Clear
  - 1 Almost Clear
  - 2 Mild
  - 3 Moderate
  - 4 Severe
- Baseline Total Lesion Counts by treatment side (trifarotene 50 μg/g versus vehicle)
- Baseline Inflammatory Lesion Counts by treatment side (trifarotene 50 μg/g versus vehicle)
- Baseline Non-Inflammatory Lesion Counts by treatment side (trifarotene 50 μg/g versus vehicle)

If ITT population and Safety population do not include the same subjects, the summary will be presented for the Safety population too.

Frequencies and proportions (n, %) of subjects will be summarized using the ITT population (females only) for the following classification category:

- Childbearing Potential
  - Strict Abstinence
  - Male/Female Condom
  - Cap, Diaphragm or Sponge with Spermicide
  - Combined (estrogen and progestogen containing) Oral, Intra-vaginal or Transdermal Hormonal Contraception

- Injectable or Implanted Hormonal Contraception
- Intra-Uterine Devices
- Vasectomized partner for at least 3 months prior to the Screening visit
- Other
- Non-childbearing Potential
  - Post-Menopausal

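### A cheap improvement, not an error: the primary test fixes the coefficient of the baseline side difference at 1, and no planned analysis estimates it

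*SAP*

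**What the plan says.** SAP 6.3.3 applies the paired t-test to the "bilateral difference between the trifarotene side and the vehicle side in absolute change from baseline in total atrophic acne scar counts at Week 24". Protocol 7.4.3.1 names the same test. SAP 6.1.1 introduces its formulas with "Absolute change from baseline and percent change from baseline will be calculated as follows" and defines absolute change as the post-baseline value minus the baseline value. SAP 6.3.6.1 then says: "No adjustment for covariates is planned for the primary, secondary and exploratory efficacy analyses".

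SAP 6.3.4 opens its list with "To assess the robustness of the primary efficacy results, the following sensitivity analyses will be conducted" and gives four: jump-to-reference, LOCF, observed cases and per protocol. Each changes how missing data are handled or who is included, and none adds a baseline term. Baseline counts do enter the imputation regression in SAP 6.3.6.2, but that model is fitted separately by treatment and only fills gaps.

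The covariate itself is available: SAP 6.2.5 lists "Baseline Total Atrophic Acne Scar Counts by treatment side". Protocol 5.3.2 lets one half-face carry up to twice as many scars as the other, so the baseline side difference need not be zero in an individual subject.

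**The concern.** If the Week 24 side difference tracks the baseline side difference one for one, subtracting the whole baseline difference is the most efficient choice. If it tracks it less than one for one, for instance because part of the baseline difference is counting error, the subtraction over-corrects and leaves removable variance in the error term. What is at stake is some precision on the primary endpoint, with no extra subjects or visits. The plan also lacks an analysis showing whether chance asymmetry at baseline, which the entry criteria permit, affects the result.

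**Working it through.** **The plan's own figure.** Inputs from SAP section 4: two-sided alpha 0.05, power 80%, difference 1.7, SD of the paired difference 6.0, drop-out 15%. At n = 100 the two t quantiles (99 df) sum to 2.829, and 2.829² × 36 / 1.7² = 99.7, which rounds up to 100. Then 100 / 0.85 = 117.6, which rounds up to 118. Both figures reproduce. Noncentral-t power at n = 100, with noncentrality 1.7 / (6.0/√100) = 2.833, is 80.1%.

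**Where the fixed coefficient comes from.** Let B be the baseline side difference (trifarotene minus vehicle) and W the Week 24 side difference. The analysed quantity is D = W − 1 × B. Suppose W regresses on B with slope b, and let sB be the SD of B. Then D regresses on B with slope b − 1, and the part of Var(D) explained by B is (1 − b)² × sB². Estimating the slope leaves residual variance 36 − (1 − b)² × sB².

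**Cost of estimating it.** One degree of freedom is lost (98 instead of 99), and the variance of the intercept is inflated by 1 + 1/(n − 3) = 1 + 1/97. If b = 1, so that nothing is gained, the noncentrality is 2.833/√(1 + 1/97) = 2.819 and power is 79.7%. That is a loss of about 0.4 points.

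**Power at 100 pairs with an estimated slope (planned test: 80.1%).** The documents give neither b nor sB, so both are assumed.

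| sB (assumed) | b = 0.9 | b = 0.8 | b = 0.7 | b = 0.5 |
|---|---|---|---|---|
| 2 | 79.75% | 79.9% | 80.1% | 80.8% |
| 3 | 79.8% | 80.1% | 80.6% | 82.2% |
| 4 | 79.9% | 80.4% | 81.3% | 84.1% |

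Example, sB = 4 and b = 0.5: the explained variance is 0.25 × 16 = 4, the residual variance 32, the SD 5.657 and the noncentrality 2.990, giving 84.1%. Over b from 0.8 to 0.5, 80% power needs 101 to 90 pairs, against 100 as planned.

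**Break-even.** Adjusted and unadjusted power are equal when the explained variance is 0.3745 of 36 (1.04%), that is when (1 − b) × sB = 0.61 scars. Adjustment therefore helps only if b is below about 0.69, 0.80 or 0.85 at sB of 2, 3 or 4.

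**Why sB stops at 4.** The 2:1 entry limit caps the side difference at 2 scars for a face total of 10 (4 and 6), 6 for a total of 20 (7 and 13) and 10 for a total of 30 (10 and 20). An SD well above 4 would need large totals.

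**Validity.** In simulations of 100 complete, normally distributed pairs (20,000 trials per setting, with b of 1, 0.8 or 0.5 and sB of 4 or 5), rejection under no effect was 4.7% to 5.2% for the planned test and 4.7% to 5.3% for the adjusted one. Neither inflates type I error.

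**The case against.** The strongest case against is that there is no defect to correct. The paired t-test on change is valid and prespecified, Protocol and SAP agree on it, and leaving out covariates is an explicit choice. That stands.

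The gain also rests on two quantities that the documents do not give, and design features push b towards 1. SAP 3.5.1 requires standardised rater training and asks that, when possible, "the same evaluator should perform the SGA, scar counts, IGA and acne lesion counts, for each subject", which limits counting error. At b = 0.9 the adjusted test is slightly worse at every sB considered. This stands too, and it is why the gain cannot be promised.

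Power is protected in other ways. The SD of 6.0 was "derived by supposing an increase of about 35% of the variability observed in study RD.03.SPR.105061". The re-estimation in SAP 4.1 ("Without unblinding the treatment assigned to each half face, we can calculate the Left-Right difference as follows") uses the upper bound of the variance, cannot go below the initial size and may rise to 160. If the true SD is nearer the earlier study's, it is 6/1.35 = 4.44 or 6/√1.35 = 5.16, depending on whether the 35% was applied to the SD or to the variance. Unadjusted power is then already 96.6% or 90.3%, and the best case (sB = 4, b = 0.5) adds 2.2 or 3.7 points.

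A reader might go further and infer that ignoring baseline asymmetry biases the test, that the trial is underpowered, or that the primary analysis must be replaced. The documents support none of these. Side is randomised within subject, so the expected baseline side difference is zero. The sample size reproduces. An uncertain gain of this size does not compel a change of primary analysis. Nor does it justify fewer subjects, since adjustment may need 101 pairs rather than 100.

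What the objection does not answer is that no planned analysis estimates the slope, and that doing so as a supportive analysis costs very little.

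**Conclusion.** The point holds as an optional precision improvement. The planned test fixes the baseline coefficient at 1, and no planned analysis, exploratory ones included, estimates it. Against 80.1% as planned, the change in power runs from about −0.4 points (b = 1) to +4.0 points (b = 0.5, sB = 4), and is within about half a point either way for most combinations with b of 0.7 or more. This rests on the plan's SD of 6.0, difference of 1.7 and 100 evaluable pairs, on assumed values of b and sB, and on complete, approximately normal data. The figures do not model the multiple imputation or the switch to the Wilcoxon test. They are sufficient to justify a prespecified supportive analysis, but do not show that the primary analysis should change.

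**What to change.** **Recommended.** Before unblinding, add a fifth prespecified analysis of the primary endpoint to SAP 6.3.4 and reword SAP 6.3.6.1 to allow it. In each imputed dataset, regress the trifarotene-minus-vehicle difference in change on the baseline trifarotene-minus-vehicle difference, test the intercept, and pool estimate and standard error with PROC MIANALYZE. Leave the covariate uncentred: the intercept is then the treatment difference at equal baseline counts, whereas centring at the sample mean would return the unadjusted estimate. The cost is a SAP revision, with the addition recorded under SAP section 7 because Protocol 7.4.3.4 lists only the four existing analyses.

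**If the sponsor prefers it as the primary analysis:**

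- Amend Protocol 7.4.3.1 and 7.4.3.2, which name the paired t-test for Week 24 and the intermediate visits, together with SAP 6.3.3, 6.3.5.1 and 6.3.6.1.
- Keep the unadjusted paired t-test as supportive.
- State that normality is checked on the regression residuals.
- State that the jump-to-reference, LOCF, observed-case and per-protocol analyses use the same regression. SAP 6.3.6.2 describes the first two as repeats of the primary analysis.
- Leave the sample size, the blinded re-estimation and the testing order unchanged.

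This route costs a protocol amendment, one degree of freedom (about 0.4 power points if b = 1) and a primary estimate that becomes model-based.
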